This study was designed to assess the potential effects of bosentan on the PK of lurbinecetin in patients with advanced malignancies. A sample size of eight patients was based on feasibility and clinical considerations. Based on previous studies, the intra-subject coefficient of variation (CV) of lurbinecetin PK parameters is estimated to be more than 30%. The precision (half-width) of the 90% CI for [(lurbinecetin + bosentan) / lurbinecetin alone] comparison on the log-scale will extend 0.389 from the observed differences in means, assuming that the intra-subject CV around 40%. This half-width corresponds to a 90% CI in the range of 70% and 147% assuming the ratio of the means equal to unity for each PK parameter. This 90% CI will be used to help with the interpretation of the results.

Plasma exposure to lurbinecetin:

Only patients who completed the study with sufficient and interpretable PK parameters will be included in the statistical comparison of plasma exposure to lurbinecetin. Descriptive statistics will be used to summarize pharmacokinetic data.

The primary parameter of interest for the statistical analysis will be plasma dose-adjusted $AUC_{(0-\infty)}$ (if data do not permit so, $AUC_{(0-t)}$ will be used) of lurbinecetin. The analysis will compare the log-transformed AUC for lurbinecetin administered in combination with bosentan (Test) to the lurbinecetin alone (Reference).

A mixed-effects model will be fit to the data with log-transformed AUC as the dependent variable, treatment (Test or Reference), period and sequence as fixed effects, and patient (sequence) as a random effect. The estimated least square means and intrasubject variability from the mixed-effects model will be used to construct 90% CIs for the difference in means on the log scale between treatments (Test or Reference). The adjusted mean differences and the 90% CIs will be exponentiated to obtain estimates of the ratio of adjusted geometric means (Test/Reference) and 90% CIs for the ratios.

[figure not shown]
A large difference (e.g. two-fold difference shown from CIs and least square means) will be considered to show evidence on whether bosentan co-administration has a clinically relevant effect on lurbinecetin exposure.

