9.2 SAMPLE SIZE

A block randomization (1:1 ratio) will be performed. At least 8 patients are expected to complete all study procedures, including the collection of sufficient and interpretable PK assessments. Although at least 8 patients will be enrolled in this study; it is estimated that complete data from eight patients will be sufficient to estimate the drug-

drug interaction of bosentan on the PK of lurbinecetin. In case of patient replacement, a new patient number will be provided and he/she will be assigned to the same sequence as the patient being replaced.

This study was designed to assess the potential effects of bosentan on the PK of lurbinecetin in patients with advanced malignancies. The 90% CI will be used to help with the interpretation of the results. A sample size of eight patients was based on feasibility and clinical considerations. Based on previous studies, the intra-subject coefficient of variation (CV) of lurbinecetin PK parameters is estimated to be more than 30%. The precision (half-width) of the 90% CI for [(lurbinecetin + bosentan) / lurbinecetin alone] comparison on the log-scale will extend 0.389 from the observed differences in means, assuming that the intra-subject CV around 40%. This half-width corresponds to a 90% CI in the range of 70% and 147% assuming the ratio of the means equal to unity for each PK parameter. This 90% CI will be used to help with the interpretation of the results.

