9.3.4 Pharmacokinetics

Plasma exposure to lurbinecetin

Only patients who completed the study with sufficient and interpretable PK parameters will be included in the statistical comparison of plasma exposure to lurbinecetin.

Descriptive statistics will be used to summarize pharmacokinetic data.

The primary parameter of interest for the statistical analysis will be plasma dose-adjusted $AUC_{(0-\infty)}$ (if data do not permit so, $AUC_{(0-t)}$ will be used) of lurbinecetin. The

analysis will compare the log-transformed AUC for lubrinedin administered in combination with bosentan (Test) to the lubrinedin alone (Reference).

A mixed-effects model will be fit to the data with log-transformed AUC as the dependent variable, treatment (Test or Reference), period and sequence as fixed effects, and patient (sequence) as a random effect. The estimated least square means and intrasubject variability from the mixed-effects model will be used to construct 90% CIs for the difference in means on the log scale between treatments (Test or Reference). The adjusted mean differences and the 90% CIs will be exponentiated to obtain estimates of the ratio of adjusted geometric means (Test/Reference) and 90% CIs for the ratios.

A large difference (e.g. two-fold difference shown from CIs and least square means) will be considered to show evidence on whether bosentan co-administration has a clinically relevant effect on lubrinedin exposure.

Secondary PK parameters

Similar models used for the primary endpoint will be fit to the data with dose-normalized $AUC_{(0-t)}$ and C_{max} and in C_l , V_{ss} and $T_{1/2}$ of lubrinedin or metabolite to parent exposure PK parameters ratio, as the dependent variable. Results will also be assessed graphically.

Plasma protein binding

A similar model used for the primary endpoint will be fit to the data with dose-normalized AUC_u as the dependent variable.

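### The planned lower 90% CI limit of 70% does not follow from the stated half-width of 0.389; with that half-width it should read 68%

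*Protocol*

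**What the plan says.** Protocol section 9.2 says that "A sample size of eight patients was based on feasibility and clinical considerations". It supports that number with a precision statement, not a power calculation. At an intra-subject CV of around 40%, the 90% CI for the Test/Reference "comparison on the log-scale will extend 0.389 from the observed differences in means". The next sentence turns this into percentages: "This half-width corresponds to a 90% CI in the range of 70% and 147% assuming the ratio of the means equal to unity". The paragraph ends: "This 90% CI will be used to help with the interpretation of the results".

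The same half-width and limits appear in the synopsis (Statistical methods, Sample size) and in SAP section 5.2.

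Protocol section 9.3.4 gives the analysis behind the interval: a mixed model for log AUC with "treatment (Test or Reference), period and sequence as fixed effects, and patient (sequence) as a random effect". The log-scale difference and its limits are then exponentiated to give a ratio of geometric means.

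**The concern.** An interval that is symmetric on the log scale and centred on a ratio of 1 has limits exp(−h) and exp(+h). One is the reciprocal of the other, whatever CV, sample size or degrees of freedom lie behind h. The limits 70% and 147% fail this test on sight, since 1/1.47 = 0.68 and 1/0.70 = 1.43.

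This interval is the plan's whole quantitative case for what eight patients can show. Bosentan is studied as a moderate CYP3A4 inducer, so a fall in lurbinectedin exposure is the expected direction. The lower limit is therefore the one a reader will look at, and it makes the precision look better than the stated half-width allows.

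**Working it through.** **Inputs**
- Two-sided 90% interval, eight evaluable patients, 1:1 allocation to sequence, intra-subject CV about 40%, ratio of means 1, half-width 0.389, limits 70% and 147% (Protocol 9.2).
- Two-period, two-sequence crossover model (Protocol 9.3.4), giving 8 − 2 = 6 residual degrees of freedom.
- Assumption: the CV of 40% was used directly as a log-scale SD of 0.40. The documents do not state an SD or degrees of freedom.

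**Step 1. Reproduce the stated half-width**

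h = t(0.95, 6) × SD × √(2/n) = 1.9432 × 0.40 × √(2/8) = 0.3886, which prints as 0.389.

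**Step 2. Exponentiate**
- Upper: exp(0.38864) = 1.47497, which prints as 147%. This agrees with the plan.
- Lower: exp(−0.38864) = 0.67798, which prints as 68%. The plan says 70%.

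**Step 3. Does rounding of the half-width explain it?**

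Values that print as 0.389 run from 0.3885 to 0.3895. Their lower limits run from exp(−0.3895) = 0.6774 to exp(−0.3885) = 0.6781, so all print as 68%.

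**Step 4. Does rounding of the limits explain it?**
- The product of the limits should be 1. The stated pair gives 0.70 × 1.47 = 1.029. Over the rounding ranges it lies between 0.695 × 1.465 = 1.018 and 0.705 × 1.475 = 1.040.
- Half-widths that print as 70% run from −ln(0.705) = 0.3496 to −ln(0.695) = 0.3638. Those that print as 147% run from ln(1.465) = 0.3819 to ln(1.475) = 0.3887. The two ranges do not overlap, so no single half-width gives both limits.

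**Step 5. Does another reading of the inputs explain it?**

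An exact CV of 40% corresponds to a log-scale SD of √ln(1 + 0.40²) = 0.385. With n = 8:

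| Log-scale SD | df | Half-width | Lower limit | Upper limit |
|---|---|---|---|---|
| 0.40 | 6 | 0.3886 | 67.8% | 147.5% |
| 0.40 | 7 | 0.3789 | 68.5% | 146.1% |
| 0.40 | 13 | 0.3542 | 70.2% | 142.5% |
| 0.40 | 14 | 0.3523 | 70.3% | 142.2% |
| 0.40 | normal | 0.3290 | 72.0% | 139.0% |
| 0.385 | 6 | 0.3743 | 68.8% | 145.4% |
| 0.385 | 7 | 0.3649 | 69.4% | 144.0% |
| 0.385 | 13 | 0.3411 | 71.1% | 140.7% |
| 0.385 | 14 | 0.3393 | 71.2% | 140.4% |
| 0.385 | normal | 0.3168 | 72.8% | 137.3% |

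No row gives 70% together with 147%. Only the first row gives the stated half-width of 0.389. A lower limit of exactly 70% would need a half-width of −ln(0.70) = 0.357 and an upper limit of 1/0.70 = 143%, which contradicts two of the three stated figures.

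**The case against.** The arithmetic is hard to contest. The case on the other side concerns how firmly the correction can be worded and how much it matters.

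- **The upper limit is fragile too.** Exponentiating the printed 0.389 gives 1.4755, or 148%. The stated 147% holds only from the unrounded 0.3886, where 1.47497 sits just under the rounding boundary. This is true, and it is a reason to state the basis. It does not help the lower limit, which is 68% either way.
- **68% is conditional on keeping 0.389.** If the sponsor meant an exact CV of 40%, the consistent figures are 0.374 and 69% to 145%. This stands as a condition on the correction. Under that reading 70% is still wrong, and so are the other two figures.
- **The basis is inferred.** The SD of 0.40 and the 6 degrees of freedom are not in the documents, so the sponsor should confirm them. They do follow from the planned model and reproduce both other stated figures.
- **The planning interval may not be used for interpretation at all.** Section 9.2 says earlier, before any half-width is given, that "The 90% CI will be used to help with the interpretation of the results". Section 9.3.4 describes the interval that will be reported: "The estimated least square means and intrasubject variability from the mixed-effects model will be used to construct 90% CIs". The closing sentence of 9.2 may therefore mean the observed interval. This is a fair reading, and it limits the consequence.
- **Nothing depends on 70%.** The sample size rests on feasibility, no decision rule uses the limit, and the example of a relevant effect is a two-fold difference. SAP section 6 leaves the PK analysis to a separate document. All of this stands and fixes the severity as minor.

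**Conclusion.** The concern holds. Given the stated half-width of 0.389, the lower limit is 68%, not 70%. The error is 2 percentage points in the favourable direction, repeated in three places across two documents. That the two limits are incompatible needs no assumption beyond a log-scale interval centred on a ratio of 1. Taking 70% as the faulty figure rests on the half-width and upper limit both reproducing with a log-scale SD of 0.40, eight patients and 6 degrees of freedom. The effect on the trial is minor: both 68% and 70% lie well inside a two-fold range, and the sample size, the model and the conclusions the trial can draw are unchanged.

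**What to change.** In the Protocol synopsis (Sample size), Protocol section 9.2 and SAP section 5.2, change 70% to 68%. Change all three together so that the documents stay in agreement. In each place add a short clause giving the basis, once the sponsor has confirmed it: log-scale SD 0.40, 6 degrees of freedom, limits computed from the unrounded half-width 0.3886. Without that clause, a reader who exponentiates the printed 0.389 will get 68% to 148% and query the upper limit.

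If an exact CV of 40% was intended, replace the whole set with a half-width of 0.374 and limits of 69% and 145%, and give the log-scale SD as 0.385.

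The cost is one number and one clause in three places. Nothing changes in the sample size, model, analysis populations or decision criterion.

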9.3 STATISTICAL ANALYSIS

Descriptive statistics (arithmetic and geometric means, median, SDev, CV% and 95% confidence interval [CI], range of value, frequencies and percentages) will be used to summarize the data.

9.3.1 Demographics

Descriptive statistics will be used to summarize the patients' baseline characteristics.

9.3.2 Safety

All AEs will be graded according to NCI-CTCAE v.5.

Treatment-emergent adverse events (TEAEs) are any adverse event aggravated in severity from baseline or having their onset between the first dose of the study drug and 31-day (± 10 days) after the last treatment dose, death or date of further therapy, whichever came first. AEs related to the study treatment or with unknown relationship occurring more than 31 days after the last dose were also taken into account as TEAEs.

Descriptive statistics will be used to characterize the profiles of drug-related AEs, drug-related deaths, SAEs, clinical laboratory data, drug-related delays and/or treatment discontinuations. Tables will be displayed by sequence and treatment (Test or Reference).

9.3.3 Efficacy

Not applicable.

9.3.4 Pharmacokinetics

Plasma exposure to lurbinecetin

Only patients who completed the study with sufficient and interpretable PK parameters will be included in the statistical comparison of plasma exposure to lurbinecetin.

Descriptive statistics will be used to summarize pharmacokinetic data.

The primary parameter of interest for the statistical analysis will be plasma dose-adjusted $AUC_{(0-\infty)}$ (if data do not permit so, $AUC_{(0-t)}$ will be used) of lurbinecetin. The

analysis will compare the log-transformed AUC for lubrinedin administered in combination with bosentan (Test) to the lubrinedin alone (Reference).

A mixed-effects model will be fit to the data with log-transformed AUC as the dependent variable, treatment (Test or Reference), period and sequence as fixed effects, and patient (sequence) as a random effect. The estimated least square means and intrasubject variability from the mixed-effects model will be used to construct 90% CIs for the difference in means on the log scale between treatments (Test or Reference). The adjusted mean differences and the 90% CIs will be exponentiated to obtain estimates of the ratio of adjusted geometric means (Test/Reference) and 90% CIs for the ratios.

A large difference (e.g. two-fold difference shown from CIs and least square means) will be considered to show evidence on whether bosentan co-administration has a clinically relevant effect on lubrinedin exposure.

Secondary PK parameters

Similar models used for the primary endpoint will be fit to the data with dose-normalized $AUC_{(0-t)}$ and C_{max} and in C_l , V_{ss} and $T_{1/2}$ of lubrinedin or metabolite to parent exposure PK parameters ratio, as the dependent variable. Results will also be assessed graphically.

Plasma protein binding

A similar model used for the primary endpoint will be fit to the data with dose-normalized AUC_u as the dependent variable.

9.3.5 Pharmacogenetics

Descriptive statistics will be used to summarize pharmacogenetic data in a separate report.

10. ADMINISTRATIVE SECTION

10.1 ETHICS

This study will be conducted in accordance with the ethical principles that have their origin in the Declaration of Helsinki ([Appendix 5](#)) and will be consistent with GCP and other applicable regulatory requirements.

The study personnel involved in conducting this study will be qualified by education, training and experience to perform their respective task(s).

The study will be conducted in compliance with the protocol. The protocol, any amendments, the patient's diary and the patient ICF will receive IEC approval/favorable opinion prior to initiation. The decision of the IEC concerning the conduct of the study will be made in writing to the Investigator and a copy of this decision will be provided to the Sponsor before commencement of the study.

The Investigator and/or the Sponsor is/are responsible for keeping the IEC informed of significant new information about the study drug.

All protocol amendments will be agreed upon by the Sponsor and the Investigator.

Administrative changes of the protocol are minor corrections and/or clarifications that have no impact on the way the study is to be conducted.

10.2 MONITORING, AUDITING AND INSPECTING

The study will be monitored by regular site visits and telephone calls to the Investigator by the clinical study monitor designated by Pharma Mar, S.A. Source document verification may be performed remotely, if required.

During site visits, the study monitor should review original patient records, drug accountability records and document retention (study file). Additionally, the monitor should observe study procedures and will discuss any problem with the Investigator.

Adequate time for these visits should be allocated by the Investigator. The Investigator should also ensure that the monitor is given direct access (as per International Conference on Harmonization [ICH] Topic E6 Guideline for Good Clinical Practice, GCP) to source documents (i.e., hospital or private charts, original laboratory records, appointment books, etc.) of the patient which support data entered in the case report forms, as defined in the ICH-GCP.

Systems and procedures will be implemented to ensure the quality of every aspect of the study.

At any time during the course or at the end of the study, the Clinical Quality Assurance Department of PharmaMar or external auditors contracted by the Sponsor may conduct an onsite or remote audit visit to the centers (ICH-GCP).

Participation in this study implies acceptance of potential onsite or remote inspections by national or foreign Competent Authorities.

10.3 PATIENT INFORMED CONSENT

The rights, safety and well-being of the trial patients are the most important considerations and should prevail over interests of science and society.

The ICF will include all elements required by ICH, GCP and applicable regulatory requirements.

Prior to inclusion into the trial, the Investigator or a person designated by the Investigator, must provide the patient with one copy of the Informed Consent Form (ICF). This copy must provide written full information about the clinical trial, in a language that is non-technical and easily understood. The Investigator should allow the necessary time for the patient or his/her legally acceptable representative to inquire about the details of the clinical study; then, the ICF must be freely signed and personally dated by the patient and by the person who conducted the Informed Consent discussion before the beginning of the study. The patient should receive a copy of the signed ICFs and any other written information provided to study patients prior to participation in the trial.

Participation in the pharmacogenetic sub-study is optional and will need an additional ICF signed by the patient. Should the patient decide not to participate in the pharmacogenetic sub-study, this will not affect his/her rights to participate in the current study.

During a patient's participation in the trial, any updates to the consent forms and any updates to the written information will be provided to him/her.

If there is a need to obtain new consent from the patients, the Investigator or a person designated by the Investigator should inform the patients of any new information

relevant to the patients' willingness to continue participation in the study, before obtaining the written consent.

10.4 CONFIDENTIALITY/ PATIENTS IDENTIFICATION

The collection and processing of personal data from patients enrolled in this study will be limited to data that are necessary to investigate the efficacy, safety, quality, and usefulness of the IMP(s) used in this study. It is the Investigator's responsibility that sufficient information pertaining to the patient's identity be retained.

The study monitor, the Sponsor's auditor, the IEC and the Competent Authorities should have direct access to all requested study-related records and agree to keep the identity of the study patients confidential.

The data must be collected and processed with adequate precautions to ensure confidentiality and compliance with applicable data privacy protection laws and regulations.

Explicit consent for the processing of personal data will be obtained from the participating patient before data collection, if applicable, and this consent should also address the transfer of the data to other entities and countries.

The Sponsor will comply with General Data Protection Regulation (GDPR) (EU) 2016/679 effective from 25 May 2018 (repealing Directive 95/46/EC of the European Parliament and of the Council of 24 October 1995), and applicable regulations on the protection of individuals with regards to the processing of personal data and on the free movement of such data.

10.5 ELECTRONIC CASE REPORT FORMS

Electronic case report forms (eCRFs) will be used to record all data for each patient. It is the responsibility of the Investigator to ensure that the eCRFs are properly and fully completed in English. ECRFs must be completed for all patients who have given informed consent and have been enrolled into the study.

A patient's source documentation comprises all medical records (including but not limited to physician/hospital notes, nurses notes, IMP preparation records including reconstitution and dilution, IMP administration records) and any original document, and as such they should be maintained at the study site.

The data collected in the eCRF will be entered into the Sponsor's databases which comply with GDPR (EU) 2016/679 effective from 25 May 2018 (repealing Directive 95/46/EC of the European Parliament and of the Council of 24 October 1995) on the protection of individuals with regard to the processing of personal data and on the free movement of such data.

10.6 INSURANCE

The Sponsor will provide insurance or indemnity in accordance with the applicable regulatory requirements.

10.7 RETENTION OF RECORDS

The Investigator/Institution should maintain study documents according to ICH Guideline for Good Clinical Practice and as required by applicable regulatory requirements.

Essential documents should be retained as per the aforementioned ICH guideline or for a longer period of time, if required by the applicable regulations.

10.8 USE OF INFORMATION AND PUBLICATION

Before the investigators of this study submit a paper or abstract for publication or otherwise publicly disclose information concerning the study drug or products, Pharma Mar, S.A. must be provided with at least 60 days to revise and approve the proposed publication or disclosure to ensure that confidential and proprietary data are protected.

If Pharma Mar, S.A. determines that patentable patient matter is disclosed in the proposed publication or disclosure, the publication or disclosure will be withheld for a period of time considered convenient. If the study is part of a multicenter study, the first publication of the study shall be made in conjunction with the presentation of a joint, multicenter publication of the study results with the investigators and the institutions from all appropriate sites that are contributing data, analysis and comments. However, if such a multicenter publication is not submitted within 12 months after conclusion, abandonment or termination of the study at all sites, the present study may be published individually in accordance with the procedure established above.

The order of the coauthors will reflect the relative contribution of each one to study development and analysis. Relevant Sponsor personnel who have fully participated in the study must be considered for co-authorship of the publication. In general, the order of the investigator will reflect who recruits the highest number of patients with information finally available for data analysis.

